6.3 HANDLING OF DERIVED VARIABLES

The baseline is considered to be the start date of the first administration of Esgliteo and the baseline value is defined as the last value measured before the first administration.

Derivation/imputation of variables will be performed as in the following.

Table 3 Derived variables

Variable	Derivation Method
Change from baseline	Post-baseline value – Baseline value
Age group	Less than 19 years 19 years or older and less than 30 years 30 years or older and less than 40 years 40 years or older and less than 50 years 50 years or older and less than 60 years 60 years or older
Duration of disease (years)	(Date of data release consent – Diagnosed date) / 365.25
Geriatric population	65 years or older, Less than 65 years
Total period of drug use(days)	End date of Esgliteo final administration – Start date of Esgliteo first administration+1 If [Continuing] is checked on CRF [DISPENSING OF ESLITEO] page, end date of Esgliteo final administration will be replaced with date of last safety assessment, and if date of last safety assessment is missing, it is replaced with date of last visit.
10/5mg, 25/5mg Sum of total period of drug use(days)	Sum of ((End date of Esgliteo administration - Start date of Esgliteo administration +1) per duration of visit) If [Continuing] is checked on CRF [DISPENSING OF ESLITEO] page, end date of Esgliteo final administration will be replaced with date of last safety assessment, and if date of last safety assessment is missing,

CONFIDENTIAL

STATISTICAL ANALYSIS PLAN

Variable	Derivation Method
	it is replaced with date of last visit.
Total number of administrations	Sum of (Administration frequency ^[1] ×period of drug use) per duration of visit [1] QD: Once a day, BID: Twice a day, TID: Three times a day, QID: Four times a day, PRN: Whenever necessary But, the value collected with PRN is excluded from analysis.
Average number of administrations per day	Total number of administrations / Total period of drug use
Duration of AE (Days)	AE end date – AE onset date +1 If [Continuing] is checked on CRF [ADVERSE EVENTS] page, AE end date will be replaced with date of last safety assessment, and if date of last safety assessment is missing, it is replaced with date of last visit, and will mark \geq (e.g. ≥ 15).
Onset duration of AE	AE onset date – Date of first Esglito administration
Less than 7% of HbA1c	yes: HbA1c $< 7\%$ no: HbA1c $\geq 7\%$

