 - Auto-amputations (i.e. spontaneous separation of non-viable portion of the lower limb)

Not included in this definition are debridement (removal of callus or dead tissue), procedures on a stump (like stump revision, drainage of an abscess, wound revision etc.) and other procedures (e.g., nail resection or removal) without a concomitant resection of a limb (amputation or disarticulation).

Adverse events leading to discontinuation refers to all adverse events in which action taken with study drug due to AE is 'Drug withdrawn'.

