8.3 SAFETY ANALYSES BY FACTORS

8.3.1 Univariate analysis

The following categorical variables will be summarized using number of subjects, the number of subjects and proportion of the number of subjects with AE and 95% confidence interval. AE Occurrence will be analyzed using Pearson's chi-square test or Fisher's exact test to determine if statistically significant differences exist. (However, if [Diabetes mellitus complications] responds with [Not applicable], [Pregnancy] responds with [Not applicable], [Height] responds with [Not done], it is excluded from Pearson's chi-square test or Fisher's exact test.)

- Gender (Male, Female)
- Smoking status (Never smoked, Ex-smoked, Currently smokes)
- Family history of T2DM (Yes, No)
- Previous allergy (Yes, No)
- Diabetes mellitus complications (Retinopathy, Neuropathy, Nephropathy, Vasculopathy, Other) (Yes, No, Not applicable)
- Medical history (Yes, No)
- Comorbidities (Yes, No)
- Prior medication (Yes, No)
- Concomitant medication (Yes, No)
- Other anti-diabetic agent (Yes, No)

For the following continuous variables AE Occurrence will be summarized using odds ratio and 95% confidence interval for an increase or decrease per defined unit of the variable based on using simple logistic regression.

- Age (years)
- Height (cm)
- Weight (kg)

CONFIDENTIAL

STATISTICAL ANALYSIS PLAN

- Duration of disease (years)
- Total period of drug use (days)
- Total number of administrations
- Average number of administration per day

Subjects of special investigation will be summarized using number of subjects, number of subjects with AE, proportion of subjects with AE and 95% confidence interval. AE Occurrence will be analyzed by using Pearson's chi-square test or Fisher's exact test to confirm statistically significant differences.

- Geriatric population (65 years or more, Less than 65 years)
- Pregnant women (Yes, No, Not applicable)
- Renal impairment (Yes, No)
- Hepatic impairment (Yes, No)
- Long term use (24 weeks or more)

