8.3.2 Multivariable analysis

As a result of simple logistic regression, statistically significant variables will be included in a multivariable logistic regression and odds ratio and 95% confidence interval will be provided for each variable. (However, Variables with the Variance Inflating Factor (VIF) exceeding 10 can be excluded from the model.) The complete case analysis will be used to handle missing values of variables in the multivariable logistic regression model.

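### SAP 8.3 tests length of drug use as a factor for AE yes/no, although AEs and early leaving themselves determine that length, so the odds ratio cannot be read as an effect of duration

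*SAP*

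**What the plan says.** SAP 6.3, Table 3, defines total period of drug use as last minus first administration date plus one day. If the patient is marked as continuing, "end date of Esgliteo final administration will be replaced with date of last safety assessment". Total number of administrations is dosing frequency times period, summed over visits. SAP 8 defines AEs leading to discontinuation as "all adverse events in which action taken with study drug due to AE is" drug withdrawn.

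SAP 8.3.1 lists seven continuous variables for simple logistic regression, for which "AE Occurrence will be summarized using odds ratio and 95% confidence interval for an increase or decrease per defined unit of the variable". Three describe exposure: total period, total number of administrations, and administrations per day. The same section tests "Long term use (24 weeks or more") by chi-square or Fisher's exact test; only one level is printed. Under SAP 8.3.2, "statistically significant variables will be included in a multivariable logistic regression and odds ratio and 95% confidence interval will be provided for each variable", the selection being made on the simple logistic regressions.

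Protocol 9.7.1 lists total period and long-term use among the parameters. Protocol 9.7.2 asks for AE tests by those data and for logistic regression on factors that may influence AE frequency, with the meaning of significant ones to be described. SAP 9.2(4), 9.4 and 9.5 use the same exposure variables for effectiveness.

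**The concern.** A factor for AE occurrence should be fixed before the AE can happen. Length of use is not, and two mechanisms act on it in opposite directions.

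- **AE-driven stopping.** An AE that leads to withdrawal ends the period. Patients with such AEs have short periods because of the AE, which pushes the odds ratio below 1.
- **Time at risk.** A patient who leaves early for another reason has a short period and, if AEs are counted only to last contact, less time in which to show one. This pushes the odds ratio above 1.

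Nothing in the SAP cuts the period at AE onset, and no person-time or time-to-event analysis is planned. Safety is the primary objective, and Protocol 9.7.2 obliges the report to explain a significant factor. A reader could be told that longer use goes with fewer AEs, or with more, when the result shows only who stopped and how leavers were counted.

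**Working it through.** The sample size of 600 is a regulatory requirement, so there is no power calculation to reproduce. The check asks what the planned test does when duration has no effect.

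**Inputs from the documents:** 600 patients; two-sided 5% tests (SAP 5.2); Visit 3 from day 168; total period as in Table 3. **Assumptions:** constant AE hazard; 20% with a first AE by day 168; Visit 3 at day 168 plus 0 to 28 days; 10% leave, uniformly over days 1 to 168; 0 to 30% of AEs stop the drug at onset.

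**1. Long-term use by hand.** The comparator is taken as under 24 weeks, since the SAP prints only one level.

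- Daily hazard = −ln(0.80)/168 = 0.001328.
- AE risk to an average Visit 3 at day 182: 1 − exp(−0.001328 × 182) = 21.5%.
- AE risk of a leaver to last contact, averaged over leaving times: 1 − (1 − 0.80)/0.2231 = 10.4%.
- 540 completers: 108 AEs by day 168, and 540 × (0.2147 − 0.20) = 7.9 afterwards. 60 leavers: 6.2 AEs to last contact, or 60 × 0.2147 = 12.9 if obtained to Visit 3.
- A stopping share q moves 108q completers with an AE into the short-use group.

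| Share of AEs stopping drug | AE %, 24 weeks or more | AE %, under 24 weeks (to last contact) | AE %, under 24 weeks (to Visit 3) |
|---|---|---|---|
| 0% | 115.9/540 = 21.5 | 6.2/60 = 10.4 | 12.9/60 = 21.5 |
| 10% | 105.1/529.2 = 19.9 | 17.0/70.8 = 24.0 | 23.7/70.8 = 33.5 |
| 20% | 94.3/518.4 = 18.2 | 27.8/81.6 = 34.1 | 34.5/81.6 = 42.3 |

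The true difference is zero in every row.

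**2. Total period by simulation** (logistic regression of AE on total period, Wald test, 1000 runs, all 600 kept):

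| Share of AEs stopping drug | 0% | 5% | 10% | 20% | 30% |
|---|---|---|---|---|---|
| AEs to last contact: rejection | 70% | 11% | 6% | 72% | 99% |
| Odds ratio per 28 days | 1.33 | 1.09 | 0.98 | 0.85 | 0.77 |
| Leavers' AEs obtained to Visit 3: rejection | 5% | 23% | 62% | 98% | 100% |
| Odds ratio per 28 days | 1.01 | 0.92 | 0.86 | 0.77 | 0.71 |

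A repeat with another seed agrees within simulation error. Counting to last contact is close to the collection window in Protocol 11.2; obtaining leavers' AEs is what Protocol 9.9.1 aims for.

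**3. Exclusions under SAP 4.2(e).** If leavers before day 84 are removed only when no AE is recorded, while AEs of the others are obtained to Visit 3, the odds ratio is about 0.72 with about 76% rejection when no AE stops the drug. That is a selection bias of its own.

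**4. Effectiveness.** With 60 to 80% improved, if 0/5/10/20% of non-improved patients stop between weeks 12 and 24, the test of total period rejects in 5/34–41/75–88/100%. With no such stopping there is no problem.

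**5. Check of the remedy.** The true first-AE rate is 0.001328 × 365.25 × 100 = 48.5 per 100 patient-years. Estimates lie between 48.3 and 51.0 for every stopping share and both ways of counting. A baseline factor with no effect is rejected in 4.2 to 5.3%. Constant hazard and non-informative leaving are built into this check, so it shows only that the method is coherent.

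**The case against.** The protocol calls all analyses descriptive, and the main safety result, the AE proportions with exact intervals in SAP 8.1, does not use these variables. The duration and long-term-use tests come from Protocol 9.7.1 and 9.7.2, so the SAP is following instructions. The SAP also reports AEs leading to discontinuation, action taken and reasons for early interruption, so a careful reader can see how often AEs end use. All of this stands and limits the reach. It does not repair a 5% test whose significant results must be explained.

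Four stronger readings are tempting, and the documents do not support them.

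- A reader might infer that the bias always makes longer use look safer. With all patients kept and AEs counted to last contact, the odds ratio is 1.33 with no AE-driven stopping and 0.98, with rejection near nominal, at 10% stopping. Lower values seen when early leavers are removed owe much to the exclusion itself, and SAP 4.2(e) removes only patients whose safety information cannot be obtained.
- A reader might infer that long-term use enters the multivariable model. SAP 8.3.2 names only variables significant in simple logistic regression, so its entry is unclear.
- Total number of administrations nearly duplicates total period under once-daily dosing, but SAP 8.3.2 already provides that "Variables with the Variance Inflating Factor (VIF) exceeding 10 can be excluded from the model".
- The absence of tablet strength from the factor lists is not a breach. Neither document requires AEs by strength, SAP 11 explains why average daily dose was replaced, and the table shells are a separate document.

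**Conclusion.** The point holds. The sign and size of the duration odds ratio, and of the long-term-use comparison, depend on stopping patterns and on how leavers are handled, not on any effect of duration. Under the assumed rates with all patients kept, false rejection runs from about the nominal level (4 to 6% across repeat runs) to 100%. These figures show the mechanism and its range; they do not predict this study's result.

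The impact is confined to the factor tables C16 to C19: duration itself sits in C17 and C18, and in C19 if carried forward. No distortion of the other factors is claimed. The effectiveness analogues are affected only if patients who do not improve stop earlier. The change should be made because safety is the primary objective and the correction is cheap, but it does not put the main AE results in doubt.

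**What to change.** 1. **Tables.** Keep the total-period and long-term-use tables that Protocol 9.7.1 and 9.7.2 call for. Show them without a test, or label them as post-baseline and not interpretable as an effect of longer use. State the comparator for long-term use. Treat SAP 9.2(4) and 9.4 the same way.
2. **Models.** Keep total period and total number of administrations out of the models in SAP 8.3.2 and 9.5. No separate collinearity rule for the pair is then needed.
3. **Added analysis.** Report first-AE rates per patient-year and time to first AE on baseline factors. Time at risk runs from first dose to first AE or end of AE observation; say whether it is on-drug or on-study.
4. **Secondary, descriptive only.** Show AEs and effectiveness by starting tablet strength, which is already collected, noting that strength follows prior treatment and need. If AEs are also shown by strength at onset, the Table 3 variable "10/5mg, 25/5mg Sum of total period of drug use(days") does not serve as a denominator for first AEs as it stands. Cut those days at first AE, and show AEs after stopping separately.

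**Cost:** a few extra tables and SAP wording. No new data are needed: dose, administration dates and AE onset are collected. SAP 1 already provides for recording a changed analysis and its reason in the final report.

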8.3.2 Multivariable analysis

As a result of simple logistic regression, statistically significant variables will be included in a multivariable logistic regression and odds ratio and 95% confidence interval will be provided for each variable. (However, Variables with the Variance Inflating Factor (VIF) exceeding 10 can be excluded from the model.) The complete case analysis will be used to handle missing values of variables in the multivariable logistic regression model.

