9.7.2 Analysis of Safety

- ① Among the subjects of safety evaluation, the number of subjects with adverse event incurred and the number of adverse events incurred should be calculated, and the frequency of adverse events and the 95% confidence interval should be presented.
- ② The number and percentage of adverse events by type and category should be presented.
- ③ Analysis should be made using Chi-square test or Fisher's Exact test on the adverse event onset status by demographic data of subjects of safety evaluation.
- ④ To estimate any factors that are thought to influence the analyzed frequency of adverse events, logistic regression analysis should be conducted, and for statistically significant parameters, the meaning should be described.

Adverse Events (AEs) excluding the AEs whose 'Causality' is "Unlikely" will be treated as AEs whose causality cannot be excluded (hereafter "Adverse Drug Reaction (ADR)").

AEs will be coded according to the latest version of Medical Dictionary for Drug Regulatory Affairs (MedDRA) coding system. Concomitant medications will be coded according to the latest version of KIMS(Korea Index of Medical Specialties) coding system. The study database will not be locked until coding is complete.

Safety analyses will be based on all patients treated, i.e. all patients who received at least one dose of Esgliteo. However, if data for patients who have been treated with Esgliteo beyond the scope of approved label are collected, separate safety analyses will be performed. Patients lost to follow up will be characterized compared to the remaining patients and reason and time point of loss to follow up will be evaluated.

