9.4 UNIVARIATE ANALYSIS

The following categorical variables will be summarized using number of subjects, number of efficacy, efficacy rate and 95% confidence interval. Efficacy will be analyzed using Pearson's chi-square test or Fisher's exact test to determine if statistically significant differences exist. (However, if [Diabetes mellitus complications] responds with [Not applicable], [Pregnancy]

CONFIDENTIAL

STATISTICAL ANALYSIS PLAN

responds with [Not applicable], [Height] responds with [Not done], it is excluded from Pearson's chi-square test or Fisher's exact test.)

- Gender (Male, Female)
- Smoking status (Never smoked, Ex-smoked, Currently smokes)
- Family history of T2DM (Yes, No)
- Previous allergy (Yes, No)
- Diabetes mellitus complications (Retinopathy, Neuropathy, Nephropathy, Vasculopathy, Other) (Yes, No, Not applicable)
- Medical history (Yes, No)
- Comorbidities (Yes, No)
- Prior medication (Yes, No)
- Concomitant medication (Yes, No)
- Other anti-diabetic agent (Yes, No)

The following continuous variables will be summarized using number of subjects. Efficacy will be summarized using odds ratio and 95% confidence interval by using simple logistic regression.

- Age (years)
- Height (cm)
- Weight (kg)
- Duration of disease (years)
- Total period of drug use (days)
- Total number of administrations
- Average number of administration per day

Subjects of special investigation will be summarized using number of subjects, number of efficacy, efficacy rate and 95% confidence interval. Efficacy will be analyzed by using Pearson's chi-square test or Fisher's exact test to determine if statistically significant differences

CONFIDENTIAL

STATISTICAL ANALYSIS PLAN

exist.

- Geriatric population (65 years or more, Less than 65 years)
- Pregnant women (Yes, No, Not applicable)
- Renal impairment (Yes, No)
- Hepatic impairment (Yes, No)
- Long-term use (24 weeks or more)

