10.5 DETAILS OF SERIOUS UNEXPECTED AEs

The details of Serious Unexpected AEs collected from use result surveillance, special study (Pharmacoepidemiology study, etc.), clinical trials and Spontaneous reporting will be presented in a listing.

11. Changes to the planned analysis method

In the 9.7.1 demographic analysis item of Protocol (version 4.0), it is described that the administration status of this drug (average daily dose) is analyzed, but since Esglito is a composite, the average number of administrations per day will be analyzed.

[figure not shown]
12. SAS program code

The following SAS program codes will be used.

Table 6 SAS program code

Analysis method	SAS program code
Pearson's chi-square test or	PROC FREQ DATA=dataset;
Fisher's exact test	TABLE ae*factor/CHISQ EXACT; RUN;
Paired t-test	PROC UNIVARIATE DATA=dataset; VAR diff;

CONFIDENTIAL

STATISTICAL ANALYSIS PLAN

Analysis method	SAS program code
	RUN;
t-test	PROC TTEST DATA=dataset; CLASS factor; VAR chg; RUN;
ANOVA	PROC MIXED DATA=dataset; CLASS treatment; MODEL variable=treatment; LSMEANS treatment / PDIFF CL; RUN;
Simple logistic regression	PROC LOGISTIC DATA=dataset; CLASS factor; MODEL ae=factor; RUN;
Multiple logistic regression	PROC LOGISTIC DATA=dataset; CLASS factor1 factor2 factor3; MODEL ae= factor1 factor2 factor3 factor4; RUN;

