13. TABLE SHELLS

The following are the lists of tables for this study.

Table 7 List of Tables

Table Number	Table Description
A1	Study period and number of subjects
A2	Post-Market Surveillance tables
B1	Demographics
B2	Disease information

CONFIDENTIAL

SD 0400 A v4.0

Statistical Analysis Plan

Protocol No.: 1275-0028

35/38 page

Effective Date: 10-Jan-2022

STATISTICAL ANALYSIS PLAN

[figure not shown]
Table Number	Table Description
B3	Subjects of special investigation
B4	Medical history
B5	Comorbidities
B6	Prior medication
B7	Concomitant medication
B8	Other anti-diabetic agent
B9	Esgliteo administration status
C1	Summary of AEs
C2	Frequency of AEs and ADRs
C3	Frequency of SAEs and SADRs
C4	Frequency of UAEs and UADRs
C5	Frequency of non-serious adverse drug reaction
C6	Frequency of AESI
C7	AEs leading to discontinuation
C8	Details of SAEs
C9	AE classified by Outcome of the event
C10	AE classified by Therapy for the event
C11	AE classified by Action taken with Esgliteo
C12	AE classified by Intensity
C13	AE classified by Causal relationship
C14	SAEs and SADRs by frequency of occurrence
C15	UAEs and UADRs by frequency of occurrence
C16	Status of AEs by subject characteristics – categorical variables
C17	Status of AEs by subject characteristics – continuous variables
C18	Status of AEs for subjects of special investigation
C19	Status of AEs by subjects of special investigation – Multivariable analysis
C20	Summary of AEs for subjects of special investigation
C21	Details of AEs for subjects of special investigation
C22	Summary of AEs for subjects who are not treated according to the approved label

CONFIDENTIAL

STATISTICAL ANALYSIS PLAN

Table Number	Table Description
C23	Details of AEs for subjects who are not treated according to the approved label
C24	Summary of AEs for subjects of long term safety set
C25	Frequency of AEs and ADRs for long term safety set
C26	Frequency of SAEs and SADRs for long term safety set
C27	Frequency of UAEs and UADRs for long term safety set
C28	Frequency of non-serious adverse drug reaction for long term safety set
C29	Frequency of AESI for long term safety set
C30	Frequency of AEs leading to discontinuation for long term safety set
C31	Details of SAEs for long term safety set
D1	Main outcome – the change of HbA1c from baseline
D2	Other outcome – HbA1c reaching less than 7% (target effectiveness response rate) from baseline

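### The entry rule for the multivariable models relies on simple logistic regression, which the SAP prose runs only for continuous variables, so categorical factors have no stated route in and the candidate list contradicts the SAP's own tables and code.

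*SAP*

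**What the plan says.** SAP 8.3.1 divides the candidate factors for adverse events into three lists.

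- Ten categorical factors, including sex and comorbidities: "AE Occurrence will be analyzed using Pearson's chi-square test or Fisher's exact test to determine if statistically significant differences exist".
- Seven continuous variables (age, height, weight, disease duration, total period of drug use, total number of administrations, average administrations per day): "For the following continuous variables AE Occurrence will be summarized using odds ratio and 95% confidence interval", obtained from simple logistic regression.
- Five special-investigation factors, including renal and hepatic impairment: "AE Occurrence will be analyzed by using Pearson's chi-square test or Fisher's exact test to confirm statistically significant differences".

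SAP 8.3.2 then gives the entry rule: "As a result of simple logistic regression, statistically significant variables will be included in a multivariable logistic regression". SAP 9.4 and 9.5 repeat the structure for effectiveness. There too the logistic method is named only under the continuous list: "Efficacy will be summarized using odds ratio and 95% confidence interval by using simple logistic regression".

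Other places point elsewhere. Table C19 in SAP section 13 is titled "Status of AEs by subjects of special investigation – Multivariable analysis". The simple logistic code in SAP section 12, Table 6, reads "CLASS factor; MODEL ae=factor; RUN", which declares a categorical predictor. The multiple logistic code there has three CLASS factors and one without CLASS. Protocol 9.7.2 sets no limit by variable type: "To estimate any factors that are thought to influence the analyzed frequency of adverse events, logistic regression analysis should be conducted". Protocol 9.7.3, item 5, asks the same for effectiveness.

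**The concern.** An entry rule should settle which variables can appear in the model before anyone sees results. Here the rule depends on an analysis that most candidates never receive, so a programmer following the prose and one following the table list and code would build different models.

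Under the prose, the model meant to identify risk factors leaves out sex, comorbidity, and renal and hepatic impairment. If such a factor both raises the risk of an event and goes with age or disease duration, part of its effect is credited to the variable that stayed in. Safety is the primary objective, and protocol 9.7.2 requires the meaning of significant parameters to be described, so a misattributed factor could reach the report with an interpretation attached.

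Two of the seven variables the prose does admit are also poor predictors of adverse events. Total period of drug use and total number of administrations are measured after baseline, and an event leading to drug withdrawal shortens both. Their odds ratios can therefore run from event to exposure.

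**Working it through.** The documents give no figure on this point, and the 600 patients are a regulatory number without power inputs, so there is nothing to reproduce. The check is a count, a comparison of passages, and an illustration on assumed inputs.

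**Count (SAP 8.3.1).** Candidates: 10 + 7 + 5 = 22. Given simple logistic regression by the prose: 7. Not given it: 10 + 5 = 15. With the five diabetes complications counted singly, the categorical list is 10 − 1 + 5 = 14, the total 14 + 7 + 5 = 26, and those without a route 14 + 5 = 19.

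**Passages side by side.**

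| Place | Can a categorical factor enter? |
|---|---|
| SAP 8.3.1 with 8.3.2; 9.4 with 9.5 | No, read literally |
| Table 6, simple and multiple logistic code | Yes (CLASS factors) |
| Table C19 | Yes (special-investigation factors) |
| Table D10 | Implied: its subject-characteristics label is shared with D7 (categorical) and D8 (continuous) |
| Protocol 9.7.2 and 9.7.3 | Yes, no restriction |

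SAP section 11, which records departures from the protocol, mentions only the average daily dose. Table 6 does not settle the matter: it names no variables, and its CLASS statement does not suit the per-unit odds ratio that 8.3.1 wants from the same method.

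**Illustration 1: false positives for age.** All inputs are assumed. n = 600; age normal, mean 58, SD 11; logit P(impairment) = −2.2 + s × (age − 58); logit P(AE) = −1.6 + ln(OR) × impairment; no true age effect; OR 2, 2.5 or 3. The model omits impairment.

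| s per year | Impairment OR per decade, exp(10s) | Age OR per decade | Age significant at 5% |
|---|---|---|---|
| 0.02 | 1.22 | about 1.02 | about 5% |
| 0.04 | 1.49 | 1.03 to 1.05 | about 6% to 8% |
| 0.08 | 2.23 | 1.07 to 1.12 | about 11% to 21% |

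At s = 0.08 and OR 3, repeat runs gave 20% to 24%. With impairment in the model, the age odds ratio is about 1.00 and the rejection rate about 5% throughout.

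**Illustration 2: a true age effect.** Assumed age odds ratio 1.20 per decade, factor prevalence 10% or 45% at mean age, large sample. Omitting a factor unrelated to age or to events leaves about 1.19 to 1.21. Omitting one related to both (factor OR 1.5 to 3) gives 1.22 to 1.49.

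**What a 5% screen admits.** Assume a 20% event rate without the factor, OR 2 and 10% prevalence, so n₁ = 60 and n₀ = 540. Then p₁ = 0.25 × 2 / (1 + 0.25 × 2) = 0.333. The pooled SE is 0.0558 and the unpooled SE 0.0632. Power = Φ[(0.1333 − 1.96 × 0.0558) / 0.0632] = Φ(0.38), about 65%. The same formula gives about 43% at 5% prevalence and 96% at 45%.

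**The case against.** The strongest reply is that the intention is plain. Table 6 puts CLASS factors in both logistic models, and C19 and D10 anticipate categorical factors. Pearson's chi-square is also the score test from a simple logistic model with that factor, so a significant chi-square could be read as meeting the rule. This stands against the claim, which a reader might infer, that these factors cannot enter at all. It does not remove the contradiction: the rule names one method, and 8.3.1 and 9.4 assign it to one list.

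Second, bias is not shown. A reader might infer that the adjusted odds ratios are confounded. That needs an omitted factor related both to an included variable and to the outcome, and the documents contain no such data. This stands; the claim has to be that they may be.

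Third, these are exploratory models in a single-arm study, and protocol 9.9.3 concedes residual confounding. Renal and hepatic impairment are still tested in 8.3.1 and summarised in 8.4 with exact intervals. This limits the stakes. However, the protocol's caveat concerns unmeasured factors, whereas these are collected at Visit 1.

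Fourth, a reader might conclude that the significance screen is itself an error and that a fixed covariate list is required. The documents do not support that: screening is a choice with known weaknesses, and a fixed list is a trade-off.

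**Conclusion.** The point holds as an internal contradiction that leaves the candidate list for both multivariable models undefined. Taken literally, the stated rule gives 15 of 22 safety factors (19 of 26 with complications split) no route in, against Table C19, the Table 6 code and protocol 9.7.2 and 9.7.3. That finding rests on the text alone.

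The consequence is conditional. On the assumed inputs, the false-positive rate for age lies between the nominal 5% and about 21%. It is near nominal if impairment rises only weakly with age and reaches the upper figure only with a steep rise and an event odds ratio of 3. No treatment-effect estimate depends on these models. The correction is still worth making, because the rule is wrong as written and cheap to repair.

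**What to change.** In SAP 8.3.2 write, in substance: *any factor in 8.3.1, whether categorical, continuous or special-investigation, that is significant in its univariate analysis is a candidate for the multivariable model.* Put the matching sentence, referring to 9.4, in 9.5. Then align the rest:

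- In Table 6, show simple logistic code with CLASS for categorical factors and without it for continuous ones.
- Make the titles and contents of C19 and D10 match the rule.
- Keep total period of drug use and total number of administrations out of the multivariable adverse-event model, or report them separately with a note that withdrawal for an event shortens them. Their univariate results can stay. The long-term-use indicator is derived from the same exposure and needs the same treatment.
- Age in years and the geriatric indicator overlap, so say which one enters.

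The cost is one sentence per section plus these edits; no new data are needed. The downside is more candidates relative to events. If 20% of 600 patients had an event (assumed), that is 120 patients with events, or 120 / 22 ≈ 5.5 per candidate before screening, so the model may need shortening by a rule stated in advance. A 5% screen will still miss some uncommon factors, as the power figures show, and the report should say so.
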